8.2 Determination of Sample Size

No formal sample size calculation was performed for this descriptive study and the sample size is based primarily on practical considerations. It is anticipated that approximately 50 subjects will be enrolled. However, with a sample size of 50 subjects, the width of the 95% exact confidence interval in case of 0, 1, 2, 3 RSV hospitalizations (i.e., event rates of 0%, 2%, 4%, 6%) would be 7.1% (lower bound 0%; upper bound 7.1%), 10.6% (0.1%; 10.6%), 13.2% (0.5%; 13.7%), 15.3% (1.2%; 16.5%), respectively.

8.3 Randomization Methods

This is not applicable for this study, as this is an open label, non-comparative study.

9.0 Ethics

9.1 Independent Ethics Committee (IEC) or Institutional Review Board (IRB)

Good Clinical Practice (GCP) requires that the clinical protocol, any protocol amendments, the Investigator's Brochure, the informed consent and all other forms of

subject information related to the study (e.g., advertisements used to recruit subjects) and any other necessary documents be reviewed by an IEC/IRB. The IEC/IRB will review the ethical, scientific and medical appropriateness of the study before it is conducted. IEC/IRB approval of the protocol, informed consent and subject information and/or advertising, as relevant, will be obtained prior to the authorization of drug shipment to a study site.

Any amendments to the protocol will require IEC/IRB approval prior to implementation of any changes made to the study design. The investigator will be required to submit, maintain and archive study essential documents according to ICH GCP.

Any serious adverse events that meet the reporting criteria, as dictated by local regulations, will be reported to both responsible Ethics Committees and Regulatory Agencies, as required by local regulations. During the conduct of the study, the investigator should promptly provide written reports (e.g., ICH Expedited Reports, and any additional reports required by local regulations) to the IEC/IRB of any changes that affect the conduct of the study and/or increase the risk to subjects. Written documentation of the submission to the IEC/IRB should also be provided to AbbVie.

9.2 Ethical Conduct of the Study

The study will be conducted in accordance with the protocol, International Conference on Harmonization (ICH) guidelines, applicable regulations and guidelines governing clinical study conduct and the ethical principles that have their origin in the Declaration of Helsinki. Responsibilities of the clinical investigator are specified in [Appendix A](#).

9.3 Subject Information and Consent

The investigator or his/her representative will explain the nature of the study to the parent(s)/legal guardian(s), and answer all questions regarding this study. Prior to any study-related procedures being performed on the subject, the informed consent statement will be reviewed and signed and dated by the parent(s)/legal guardian(s), the person who administered the informed consent, and any other signatories according to local

requirements. For children with 2 parents, at least one must sign the consent, stating that the other parent does not object. A copy of the informed consent form will be given to the subject's parent(s)/legal guardian(s), and the original will be placed in the subject's medical record. An entry must also be made in the subject's dated source documents to confirm that informed consent was obtained prior to any study-related procedures and that the parent(s)/legal guardian(s) received a signed copy.

Information regarding incentives for subjects and information regarding provisions for treating and/or compensating subjects who are harmed as a consequence of participation in the study can be found in the informed consent form.

The study patient card should be provided to the subject's parent(s)/legal guardian(s) after the informed consent process.

10.0 Source Documents and Case Report Form Completion

10.1 Source Documents

Source documents are defined as original documents, data and records. This may include hospital records, clinical and office charts, laboratory data/information, subjects' diaries or evaluation checklists, pharmacy dispensing and other records, recorded data from automated instruments, microfiches, photographic negatives, microfilm or magnetic media, and/or x-rays. Data collected during this study must be recorded on the appropriate source documents.

The investigator(s)/institution(s) will permit study-related monitoring, audits, IEC/IRB review, and regulatory inspection(s), providing direct access to source data documents.

10.2 Case Report Forms

Case report forms (CRF) must be completed for each subject screened/enrolled in this study. These forms will be used to transmit information collected during the study to AbbVie and regulatory authorities, as applicable. The CRF data for this study are being

collected with an electronic data capture (EDC) system called Rave[®] provided by the technology vendor Medidata Solutions Incorporated, NY, USA. The EDC system and the study-specific electronic case report forms (eCRFs) will comply with Title 21 CFR Part 11. The documentation related to the validation of the EDC system is available through the vendor, Medidata, while the validation of the study-specific eCRFs will be conducted by AbbVie and will be maintained in the Trial Master File at AbbVie.

The investigator will document subject data in his/her own subject files. These subject files will serve as source data for the study. All eCRF data required by this protocol will be recorded by investigative site personnel in the EDC system. All data entered into the eCRF will be supported by source documentation.

The investigator or an authorized member of the investigator's staff will make any necessary corrections to the eCRF. All change information, including the date and person performing the corrections, will be available via the audit trail, which is part of the EDC system. For any correction, a reason for the alteration will be provided. The eCRFs will be reviewed periodically for completeness, legibility, and acceptability by AbbVie personnel (or their representatives). AbbVie (or their representatives) will also be allowed access to all source documents pertinent to the study in order to verify eCRF entries. The principal investigator will review the eCRFs for completeness and accuracy and provide his or her electronic signature and date to eCRFs as evidence thereof.

Medidata will provide access to the EDC system for the duration of the trial through a password-protected method of internet access. Such access will be removed from investigator sites at the end of the site's participation in the study. Data from the EDC system will be archived on appropriate data media (CD-ROM, etc.) and provided to the investigator at that time as a durable record of the site's eCRF data. It will be possible for the investigator to make paper printouts from that media.

11.0 Data Quality Assurance

Computer logic and manual checks will be created to identify items such as inconsistent study dates. Any necessary corrections will be made to the eCRF.

13.0 Completion of the Study

The investigator will conduct the study in compliance with the protocol and complete the study within the timeframe specified in the contract between the investigator and AbbVie.

Continuation of this study beyond this date must be mutually agreed upon in writing by both the investigator and AbbVie. The investigator will provide a final report to the IEC/IRB following conclusion of the study, and will forward a copy of this report to AbbVie or their representative.

The investigator must retain any records related to the study according to local requirements. If the investigator is not able to retain the records, he/she must notify AbbVie to arrange alternative archiving options.

AbbVie will select the signatory investigator from the investigators who participate in the study. Selection criteria for this investigator will include level of participation as well as significant knowledge of the clinical research, investigational drug and study protocol. The signatory investigator for the study will review and sign the final study report in accordance with the European Agency for the Evaluation of Medicinal Products (EMA) Guidance on Investigator's Signature for Study Reports.

The end-of-study is defined as the date of the last subject's follow-up contact, which is defined as 100 days following the final injection of palivizumab.

Appendix A. Responsibilities of the Clinical Investigator

Clinical research studies sponsored by AbbVie are subject to the Good Clinical Practices (GCP) and local regulations and guidelines governing the study at the site location. In signing the Investigator Agreement in Section 14.0 of this protocol, the investigator is agreeing to the following:

1. Conducting the study in accordance with the relevant, current protocol, making changes in a protocol only after notifying AbbVie, except when necessary to protect the safety, rights or welfare of subjects.
2. Personally conducting or supervising the described investigation(s).
3. Informing all subjects, or persons used as controls, that the drugs are being used for investigational purposes and complying with the requirements relating to informed consent and ethics committees (e.g., independent ethics committee [IEC] or institutional review board [IRB]) review and approval of the protocol and amendments.
4. Reporting adverse experiences that occur in the course of the investigation(s) to AbbVie and the site director.
5. Reading the information in the Investigator's Brochure/safety material provided, including the instructions for use and the potential risks and side effects of the investigational product(s).
6. Informing all associates, colleagues, and employees assisting in the conduct of the study about their obligations in meeting the above commitments.
7. Maintaining adequate and accurate records of the conduct of the study, making those records available for inspection by representatives of AbbVie and/or the appropriate regulatory agency, and retaining all study-related documents until notification from AbbVie.
8. Maintaining records demonstrating that an ethics committee reviewed and approved the initial clinical investigation and all amendments.

9. Reporting promptly, all changes in the research activity and all unanticipated problems involving risks to human subjects or others, to the appropriate individuals (e.g., coordinating investigator, institution director) and/or directly to the ethics committees and AbbVie.
10. Following the protocol and not make any changes in the research without ethics committee approval, except where necessary to eliminate apparent immediate hazards to human subjects.

Appendix C. Study Activities

Activity	Visit 1 Enrollment	Visit 2	Visit 3	Visit 4 ^a	Visit 5 ^b /ET	Follow-Up Contact 1 ^c	Follow-Up Contact 2 ^c
Timelines and Allowance Window^d	Day 0 Baseline	Day 30 (-5 Days)	Day 60 (±5 Days)	Day 90 (±5 Days)	Day 120 (±5 Days)	Last Prophylaxis Visit + 30 Days (+5 Days)	Last Prophylaxis Visit + 100 Days (+5 Days)
Informed Consent	X						
Provide subject card	X						
Medical and Birth History	X						
Prior ^e /Concomitant Medication	X	X	X	X	X	X	X
In-/Exclusion Criteria	X						
Assignment of Subject Number	X						
Demographics and Social History	X						
Physical Examination & Weight	X	X	X	X	X		
Body Length/Height	X						
Vital Signs ^f (HR, BP, RR, T°C)	X	X	X	X	X		
Monitor Adverse Events ^g	X ^g	X	X	X	X	X	X
Study Drug administration ^h	X ^h	X	X	X	X		
RSV Diagnostic Test ⁱ							
Assessment of RSV-Hospitalizations		X	X	X	X	X	X

ET = Early Termination

- a. Only applicable to subjects enrolled during November 2016 through December 2016.
- b. Only applicable to subjects enrolled during November 2016.

- c. Telephone contact by Investigator/designee.
- d. Allowance window is given in parentheses.
- e. Will be collected for medications given 2 weeks prior to enrollment.
- f. Vital signs to be measured prior to and 30 minutes after administration of study drug.
- g. SAEs to be registered from the time the study informed consent is signed.
- h. Only applicable to subjects fulfilling Inclusion/Exclusion Criteria.
- i. In case of a cardiac/respiratory hospitalization or deterioration in cardiac/respiratory status in a hospitalized infant, an RSV diagnostic test will be done as soon as possible, but not later than 48 hours of hospitalization.

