5.3 Effectiveness and Safety Assessments/Variables

5.3.1 Effectiveness and Safety Measurements Assessed and Flow Chart

The number of RSV hospitalizations registered during the study (detailed explanation is in Section 5.3.2.1) will be assessed for effectiveness.

Safety measurements will be based on the safety parameters monitored during the study and collected adverse events.

The following hospitalization data will be collected in the eCRF and recorded in the subject's source:

Upon any admission to hospital, the date, time and reason for admission must be recorded. The amount of supplemental oxygen must be recorded where applicable. In cases of a cardiac/respiratory illness admission, the Investigator/designee must obtain respiratory secretions within 2 days of admission for RSV detection. For cardiac/respiratory hospitalizations, a cardiac evaluation of the subject must be done and any lower respiratory tract illness signs and symptoms present (retractions, rhonchi, wheezing, crackles or rales), must be recorded, including any associated signs and symptoms as coryza, fever, apnea.

If there is evidence of new onset of respiratory/cardiac symptoms in an already hospitalized child, the Investigator/designee must assess the cardiac/respiratory illness of the subject and record any lower respiratory tract illness signs and symptoms present (retractions, rhonchi, wheezing, crackles or rales) including any associated signs and symptoms as coryza, fever, apnea. Any cardiac deterioration as indicated by unplanned or early cardiac surgery, interventional catheterization or extensive additional medical management of the cardiac condition must be recorded. New requirements or an increase in supplemental oxygen from prior to the onset of cardiac/respiratory symptoms or the need for new or additional mechanical ventilation must be also be recorded. In cases where a cardiac/respiratory deterioration is diagnosed in an already hospitalized child, the

Investigator/designee must obtain respiratory secretions for the RSV detection within 48 hours of the new onset of cardiac/respiratory symptoms.

In cases of cardiac/respiratory hospitalization or deteriorations any supplemental oxygen, ICU admissions or mechanical ventilation must be recorded if applicable.

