A complete physical examination will be performed at visits specified in [Appendix C](#). A symptom-directed physical examination may be performed at any other visit, when necessary. Any significant physical examination findings after the first dose of study drug will be recorded as adverse events.

Body Length/Height

The Investigator/designee will measure body length/height as indicated in the visit schedule in [Appendix C](#) and record the information in the subject's source and the eCRF.

Vital Signs

At each of the on-site study visits, vital signs will be taken prior to the study drug injection and repeated at 30 minutes after the study drug injection.

Assessment of RSV Hospitalizations

At every subject visit during treatment up to the follow up phone contact 1, the investigator/designee will follow-up on any subject hospitalizations for respiratory and/or cardiac reasons or any onset of new respiratory and/or cardiac symptoms in an already hospitalized subject with the parent(s)/legal guardian(s). The investigator/designee will follow the documentation requirements for RSV hospitalizations and take a note in the subject's source.

In case of cardiac/respiratory hospitalization, an RSV test might be taken by the investigator or designee if the test can be conducted within 48 hours of the hospitalization.

Follow-Up Phone Contact 1

The contact will be performed via telephone. The contact date is calculated as the date of the last prophylaxis visit (LPV) +30 Days (+5 day window is allowed). This telephone

contact will also be performed in all subjects discontinued from the study (unless the reason for discontinuation is withdrawal of consent).

The following procedures will be performed during the telephone call:

1. Record all adverse events (serious and nonserious) in source documents and on the appropriate CRF. Report SAE(s) within 24 hours of becoming aware of the SAE(s).
2. Record all concomitant medications.
3. Collect information about hospitalizations, if applicable.

Follow-Up Phone Contact 2

The contact will be performed via telephone. The contact date is calculated as the date of the last prophylaxis visit (LPV) +100 Days (+5 day window is allowed). This telephone contact will also be performed in all subjects discontinued from the study (unless the reason for discontinuation is withdrawal of consent).

The following procedures will be performed during the telephone call:

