1. Record all adverse events (serious and nonserious) in source documents and on the appropriate CRF. Report SAE(s) within 24 hours of becoming aware of the SAE(s).

RSV Diagnostic Test

In case of a respiratory/cardiac hospitalization or prolongation of existing hospitalization associated with respiratory/cardiac symptoms (Section 5.3.2.1), the investigator or designee will obtain a respiratory secretion specimen by nasopharyngeal swab, nasopharyngeal lavage or aspiration for RSV detection. Tracheal secretions may be obtained in cases when a child is intubated. The specimen will be collected as soon as possible, within 48 hours of a respiratory/cardiac hospitalization or new

respiratory/cardiac symptoms in a hospitalized infant. Respiratory secretions in all cases of a respiratory/cardiac hospitalization or prolongation of existing hospitalization associated with respiratory/cardiac symptoms will be collected using nasopharyngeal lavage or aspiration technique (see below for details) as described and tested in a central laboratory for RSV using a validated real-time RT-PCR RSV diagnostic test.

In the event of acute respiratory/cardiac hospitalization at a hospital other than the study site, parent(s)/legal guardian(s) are requested to inform the study site immediately. The Investigator or designee must make arrangements to collect a respiratory secretion specimen for RSV testing as soon as possible, but no later than 48 hours following the admittance of the subject to the non-enrolling hospital. Permission will be sought in the consent form for examination of medical records from all such hospitalizations.

The parent(s)/legal guardian(s) will be instructed that the study site will be the preferred place to obtain a respiratory secretion specimen for RSV detection in the case of hospitalization.

Collection of Nasopharyngeal Specimen for RSV Testing

Specimen collection for RSV diagnostic testing may include either of the following techniques. The goal is to obtain a specimen containing epithelial cells and not simply exudate from the nares:

- Nasopharyngeal Swab Method
- Nasopharyngeal Wash: Syringe Method
- Nasopharyngeal Wash: Bulb Method
- Vacuum-assisted Nasopharyngeal Aspirate Method

Follow the instructions outlined in the central lab manual to obtain a specimen using the site preferred method.

Central Laboratory

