5.6.2 Appropriateness of Measurements

Regular vital signs measurements (HR, BP, RR and body temperature), physical examinations and weight measurements will be performed to ensure subject's safety. These measurements used in this study are currently accepted methods of assessing pediatric subjects.

All hospitalizations will be assessed in terms of relationship to RSV to ensure the quality of primary variable data collection. Cardiac/respiratory illness as the cause of hospitalization or deterioration of subject's condition during ongoing hospitalization will be regarded as potentially related to RSV, and in these subjects, an RSV diagnostic test will be performed.

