### RSV Hospitalizations

An RSV hospitalization is defined as either 1) a respiratory/cardiac hospitalization with a positive RSV test, 2) new onset of respiratory/cardiac symptoms in an already hospitalized child, with an objective measure of worsening respiratory/cardiac status and a positive RSV test, or 3) death, which can be demonstrated as caused by RSV (by autopsy or clinical history and virologic evidence). To be considered a valid RSV test, the respiratory secretions for the RSV detection must have been collected within 2 days of admission or of worsening of respiratory/cardiac symptoms, respectively.

A hospital admission or a new onset of nosocomial respiratory/cardiac symptoms without an RSV test result will not be counted as RSV-hospitalization in the primary analysis.

Only RSV-associated hospital admissions, new onset of nosocomial respiratory/cardiac symptoms with a positive RSV test, and RSV-associated deaths occurring from the first dose of study drug injection to within 30 days of the last study drug dose will be included in the analyses for the primary endpoint.

The primary analysis will be the calculation of the number and proportion of subjects with RSV hospitalization along with the two-sided 95% exact confidence interval according to Clopper Pearson for the proportion.

In addition, a cross tabulation of reason for hospitalization or type of illness for already hospitalized subjects with new onsets of nosocomial respiratory/cardiac symptoms

[cardiac, respiratory, both] versus result of RSV text [positive, negative, not performed] will be done.

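### The protocol contradicts itself on whether the RSV test is required and when its 48-hour limit starts, so sites may leave possible primary-endpoint episodes unsampled

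*Protocol*

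**What the plan says.** Five places in the protocol and one in the SAP govern the RSV test.

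- **Protocol 5.3.1.** For a cardiac/respiratory admission, "the Investigator/designee must obtain respiratory secretions within 2 days of admission for RSV detection". For a child already in hospital, the "Investigator/designee must obtain respiratory secretions for the RSV detection within 48 hours of the new onset of cardiac/respiratory symptoms".
- **Protocol 5.3.1.1, Assessment of RSV Hospitalizations.** For a cardiac/respiratory hospitalization, "an RSV test might be taken by the investigator or designee if the test can be conducted within 48 hours of the hospitalization".
- **Protocol 5.3.1.1, RSV Diagnostic Test.** "The specimen will be collected as soon as possible, within 48 hours of a respiratory/cardiac hospitalization", or of new symptoms in an infant already in hospital. Specimens are tested in a central laboratory.
- **Protocol 5.6.2.** Where a cardiac/respiratory illness is the cause of admission or of in-hospital worsening, "an RSV diagnostic test will be performed".
- **Protocol Appendix C, footnote i.** The footnote names both admissions and in-hospital deteriorations and gives them a single limit: "an RSV diagnostic test will be done as soon as possible, but not later than 48 hours of hospitalization".
- **SAP 10.2.** For a test to be valid, the secretions "must have been collected within 2 days of admission or of worsening of respiratory/cardiac symptoms, respectively".

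The test matters because in-hospital deterioration with a positive test is the second limb of the RSV-hospitalization definition (Protocol 5.3.2.1 and 8.1.3, SAP 10.2). Protocol 8.1.3 and SAP 10.2 also state that an admission or in-hospital onset with no RSV test result is not counted in the primary analysis.

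**The concern.** A site meets different instructions depending on which page it reads. They differ on three things: whether a test is required at all, when the limit starts for a child already in hospital, and whether the limit applies to taking the specimen or to running the test.

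The two outlying sentences act on different episodes. The optional wording in 5.3.1.1 concerns cardiac/respiratory admissions. The footnote concerns deteriorations that begin more than 48 hours after admission: read literally, its deadline has already passed when the symptoms start. Such stays are foreseeable. Infants in hospital at entry are eligible if discharge is expected within 14 days (exclusion criterion 1), and the protocol provides for cardiac surgery during the study (5.1, 5.5).

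An episode with no specimen scores as a non-event, so the error can only lower the RSV-hospitalization proportion. The study has no control arm against which such a loss could be judged.

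**Working it through.** **1. The instructions side by side.**

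| Place | Obligation | What is timed | Limit runs from |
|---|---|---|---|
| Protocol 5.3.1, admission | mandatory | collection | admission (2 days) |
| Protocol 5.3.1, in-hospital deterioration | mandatory | collection | new symptoms (48 h) |
| Protocol 5.3.1.1, Assessment of RSV Hospitalizations | optional, conditional | test | hospitalization (48 h) |
| Protocol 5.3.1.1, RSV Diagnostic Test | mandatory | collection | hospitalization or new symptoms (48 h) |
| Protocol 5.6.2 | mandatory | test | no limit given |
| Appendix C, footnote i | mandatory | test | hospitalization, for both situations (48 h) |
| SAP 10.2 | validity rule | collection | admission or worsening (2 days) |

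Protocol 5.3.1, the RSV Diagnostic Test text and SAP 10.2 agree in substance. The third row is alone on obligation. Footnote i is alone in expressly covering deteriorations while naming only hospitalization as the start.

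**2. One episode traced through.** An infant admitted for a non-cardiac, non-respiratory reason develops respiratory symptoms on day 6. Under Protocol 5.3.1 a specimen is due within 48 hours of those symptoms. Under SAP 10.2 that specimen is valid. Under the literal footnote the limit ended 48 hours after admission. If no specimen is taken, Protocol 8.1.3 and SAP 10.2 do not count the episode.

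**3. The plan's own intervals.** Inputs: n = 50 (Protocol 8.2, SAP 4.3) and two-sided 95% Clopper-Pearson limits (SAP 10.2). With B the beta quantile, lower = B(0.025; x, n − x + 1), set to 0 for x = 0, and upper = B(0.975; x + 1, n − x).

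| Events | Estimate | Recomputed | Stated in plan |
|---|---|---|---|
| 0 | 0% | 0 to 7.11% | 0 to 7.1% |
| 1 | 2% | 0.05 to 10.65% | 0.1 to 10.6% |
| 2 | 4% | 0.49 to 13.71% | 0.5 to 13.7% |
| 3 | 6% | 1.25 to 16.55% | 1.2 to 16.5% |

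The stated figures reproduce, with differences from rounding only.

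**4. Losing one event (illustration).** One event is 1/50 = 2 percentage points. Going from two counted events to one moves 4% (upper limit 13.7%) to 2% (10.6%). Going from one to none moves 2% (10.6%) to 0% (7.1%).

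**5. Expected counts.** The two placebo-controlled trials in Protocol 3.0 report 4.8% and 5.3% on palivizumab. Taking these as a guide only, 50 × 0.048 = 2.4 and 50 × 0.053 = 2.65 events, so one event is 1/2.65 = 38% to 1/2.4 = 42% of the expected total.

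The documents do not say what share s of events might go untested. Treating s as an assumption, the chance of observing no events is (1 − p(1 − s))^50:

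| p | s = 0 | s = 10% | s = 25% | s = 50% |
|---|---|---|---|---|
| 4.8% | 8.5% | 11.0% | 16.0% | 29.7% |
| 5.3% | 6.6% | 8.7% | 13.2% | 26.1% |

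**The case against.** The case for leaving the text alone has real force.

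- **The footnote can be read leniently.** It orders a test for deteriorations, and Protocol 5.3.2.1 and SAP 10.2 treat an in-hospital deterioration as a cardiac/respiratory hospitalization. On that reading the 48 hours start at the deterioration. This is possible, but the footnote lists the two situations separately, so a site reading only the schedule has no cue to take it that way.
- **The fuller text is right.** Section 5.3.1.1 describes Appendix C as the outline and itself as the detail. That helps with the footnote. It does not help with the optional sentence, which is in 5.3.1.1 too and conflicts with the RSV Diagnostic Test text there.
- **The optional sentence is about asking parents at visits**, when the window may already have closed. That explains the conditional wording but does not remove the conflict with 5.3.1. The sentence also covers only cardiac/respiratory hospitalizations, so it does not reach the day-6 infant above unless the deterioration is itself treated as a hospitalization.
- **Missing tests will be visible.** The SAP 10.2 cross-tabulation has a category for tests not performed. That shows the gap among recorded episodes, but they still count as non-events.
- **The analysis is descriptive**, with no hypothesis or threshold, so no decision rule is affected. This stands and limits the severity.

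A reader might go further and infer that a late deterioration can never yield a valid test. The documents do not support that: validity is set only in SAP 10.2, which accepts a specimen taken within 2 days of worsening. A reader might also infer that admissions go untested when the central laboratory takes more than 48 hours. No turnaround time is given, and nothing tells a site to withhold a specimen for that reason.

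**Conclusion.** The contradiction stands and should be corrected. The analysis rule is sound; the weakness is in the instructions to sites. A site that follows the optional sentence in 5.3.1.1 or the literal footnote may take no specimen, and the primary analysis then scores the episode as no RSV hospitalization.

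The direction is downward and the size is unknown. The shift of 2 percentage points per lost event assumes that the episode was RSV-positive, that the site followed one of the two outlying sentences, and that the subject had no other counted RSV event, because the endpoint is per subject. RSV deaths are a separate limb. Loss is possible, not certain, and no sample-size figure changes. With roughly two to three events expected at the cited rates, even one missed specimen would be noticeable.

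**What to change.** Reword the optional sentence in Protocol 5.3.1.1 (Assessment of RSV Hospitalizations) and Appendix C footnote i so that both state the rule already in 5.3.1, the RSV Diagnostic Test text and SAP 10.2. A respiratory specimen must be collected within 48 hours of a cardiac/respiratory admission or, in a child already in hospital, within 48 hours of the onset of new respiratory or cardiac symptoms. State that the limit applies to collecting the specimen, not to completing the test.

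The cost is two sentences. No procedure, visit or analysis is added, because 5.3.1 already requires the specimen and SAP 10.2 needs no change. Make the change by protocol amendment with the IEC/IRB approval that Protocol 9.1 requires.
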